Investigator(s)/Study Center(s):	This study will be conducted at approximately 98 study sites in the Americas and Europe. Worldwide Clinical Trials, a contract research organization, will oversee operational aspects of this study on behalf of AgeneBio, Inc., the sponsor of the study.	
Phase of Development:	Phase 2B	
Objectives:	The objectives of this study are as follows:	
	Primary objective	
	To assess the efficacy of AGB101 (low-dose levetiracetam, 220 mg, extended release tablet) compared to placebo in subjects with mild cognitive impairment (MCI) due to Alzheimer's disease (AD) using Clinical Dementia Rating-Sum of Boxes (CDR-SB) scores.	
	Secondary objectives	
	To assess the efficacy of AGB101 compared to placebo on daily functioning and cognition using Functional Activities Questionnaire (FAQ) and Mini Mental State Examination (MMSE) scores.	
	To assess the effect of AGB101 compared to placebo on neuronal injury, as measured by a change in the entorhinal cortex (EC) thickness, using magnetic resonance imaging (MRI).	
	Additional secondary objectives	
	To assess the efficacy of AGB101 compared to placebo using CDR (global, memory box), Behavioral Pattern	

Confidential Page 3 of 95

	Separation-Object (BPS-O) task, and International Shopping List Test (ISLT) scores.
	To assess the effect of AGB101 compared to placebo on hippocampal volume using MRI.
	• To assess the effect of AGB101 compared to placebo on the levels of tau protein in the brain using the tau positron emission tomography (PET) marker 6-[¹⁸ F]fluoro-3-(1H-pyrrolo[2,3-c]pyridin-1-yl)isoquinolin-5-amine ([¹⁸ F]MK-6240) in a subpopulation of approximately 56 subjects.
	Exploratory Objective
	To assess the effect of AGB101 on blood-based biomarkers of neurodegeneration using samples collected at week 78 or the early termination visit.
	Exploratory Objective (optional procedure to be performed only at Johns Hopkins University)
	To assess the efficacy of AGB101 compared to placebo on hippocampal overactivity in subjects with MCI due to AD.
	Safety objective
	To assess the safety and tolerability of AGB101 compared to placebo in subjects with MCI due to AD.
Study Design:	This is a multicenter, randomized, double-blind, placebo- controlled, 78-week, fixed-dose study evaluating AGB101 versus placebo as a treatment for slowing the progression of MCI due to AD.
Planned Sample Size:	A total of 160 subjects will be randomized (80/treatment group).
Subject Selection	Eligibility criteria
Criteria:	Inclusion criteria
	Subjects must meet all of the following inclusion criteria at screening:
	1. Subjects between 55 and 85 years old (inclusive) in good general health:

Confidential Page 4 of 95

- a. Willing and able to consent and participate for the duration of the study.
- b. Have eighth-grade education or good work history sufficient to exclude mental retardation.
- c. Have visual and auditory acuity adequate for neuropsychological testing.
- d. Have proficient fluency of the native local language to participate in all the neuropsychological test assessments.
- 2. Have a study partner who has sufficient contact with the subject to be able to provide assessment of memory changes, who can accompany the subject to the screening and all major clinic visits for the duration of those visits, and who is able to provide an independent evaluation of the subject's functioning.
- 3. Have MCI due to AD as defined by all of the following criteria and consistent with the National Institute on Aging-Alzheimer's Association criteria:
 - a. MMSE scores between 24 and 30 (inclusive; exceptions may be made for subjects with < 8 years of education at the discretion of the sponsor).
 - b. A memory complaint reported by the subject or his/her study partner.
 - c. Evidence of lower memory performance based on the delayed recall portion of the ISLT.
 - d. A Clinical Dementia Rating (CDR) score of 0.5 with a memory box score of \geq 0.5.
 - e. Essentially preserved activities of daily living.
 - f. Cognitive decline not primarily caused by vascular, traumatic, or medical problems (alternative causes of cognitive decline are ruled out).
- 4. Permitted medications:
 - a. With potential pro-cognitive effects, such as cholinesterase inhibitors and memantine, must be at a stable dose for ≥ 3 months prior to screening and

Confidential Page 5 of 95

- expected to remain stable throughout the study; estrogen replacement therapy, Ginkgo biloba, and vitamin E must be at a stable dose for ≥ 4 weeks prior to screening and expected to remain stable throughout the study.
- b. Other psychotropics, such as antidepressants and antipsychotics, must be at a stable dose for ≥ 3 months prior to screening and expected to remain stable throughout the study.
- 5. Willing and able to undergo imaging procedures:
 - a. An amyloid-imaging PET scan with Neuroceq (florbetaben), Amyvid (florbetapir) or Vizamyl (flutemetamol) ([¹⁸F] isotope diagnostic agents) or documented evidence of an amyloid-positive PET scan.
 - The amyloid PET scan performed at baseline must be read by a qualified physician with experience in reading amyloid PET scans, and it should be consistent with the presence of amyloid plaques.
 - b. Repeated MRI scans (3 Tesla) with no contraindications to MRI.
 The MRI scan performed at baseline must be read by a physician with experience in evaluating brain-imaging studies in dementia. MRI scan results are consistent with the diagnosis of amnestic MCI due to AD with no clinically significant findings of non-AD pathology that could account for the observed cognitive impairment.
- 6. Willing to allow collection of blood for apolipoprotein E (ApoE) genotyping (all sites).

Exclusion criteria

Subjects must not meet any of the following exclusion criteria at screening:

1. Use of anticonvulsant medications or excluded psychotropic medications within 3 months prior to the baseline visit.

Confidential Page 6 of 95

- 2. Participation in a therapeutic clinical study for any medical or psychiatric indications within 3 months (6 months for biologics) of the screening visit, or at any time during the study.
 - Subjects must understand that they may only enroll in this clinical study once; they may not enroll in any other clinical study while participating in the current study, and they may not participate in a clinical study of a drug, biologic, therapeutic device, or medical food, in which the last dose/administration was received within 3 months (6 months for biologics) prior to screening.
- 3. History of hypersensitivity or lack of tolerability to AGB101 (levetiracetam).
- 4. Severe renal impairment (creatinine clearance of < 30 mL/minute) or undergoing hemodialysis.
- 5. Any significant neurological disease other than suspected incipient AD, such as Parkinson's disease, multi-infarct dementia, Huntington's disease, normal pressure hydrocephalus, brain tumor, progressive supranuclear palsy, seizure disorder (lifetime history; infant febrile seizures are not exclusionary), subdural hematoma, multiple sclerosis, or history of significant head trauma followed by persistent neurologic deficits, or known structural brain abnormalities.
- 6. Presence of pacemakers, aneurysm clips, artificial heart valves, ear implants, metal fragments, or foreign objects in the eyes, skin, or body that constitute a contraindication to having an MRI scan.
- 7. Diagnosis of bipolar disorder, or major depression within the past 3 years, as described in the Diagnostic and Statistical Manual of Mental Disorders, 5th Ed (DSM-5). Psychotic features, agitation, or behavioral problems within the last 3 months that could lead to difficulty complying with the protocol. Subjects must not have a major depressive disorder or other types of depression that could confound diagnosis of MCI due to AD, or clinical assessments, in the opinion of the investigator. The Geriatric Depression Scale (long form score > 9 suggests

Confidential Page 7 of 95

- depression) results should be reviewed by the investigator to assist in this determination.
- 8. Modified Hachinski Ischemic Scale (HIS) score > 4.
- 9. History of schizophrenia (DSM-5 criteria).
- 10. History of alcohol or substance abuse or dependence within the past 3 years (DSM-5 criteria).
- 11. Any significant systemic illness or unstable medical condition that could lead to difficulty in complying with the protocol requirements.
- 12. Any unstable medical condition that is likely to require new medical or surgical treatment during the course of the study and where such treatments might affect the collection of efficacy data.
- 13. Clinically significant abnormalities in B12 or thyroid function test that might interfere with the study.

 A low B12 (below normative range for elderly) is exclusionary, unless follow-up labs (homocysteine and methylmalonic acid) indicate that it is not physiologically significant. If the B12 deficiency is treated, subjects may become eligible to participate in the study.
- 14. Residence in a skilled nursing facility.

 Individuals in independent living communities, assisted living facilities, residential care facilities, or continuing care communities are eligible provided they engage in a sufficient spectrum of activity to permit assessment of all 6 domains contributing to the Clinical Dementia Rating-Sum of Boxes (CDR-SB). Individuals in these facilities must also have a study partner who has the ability to observe the subject during the study and can participate in clinical evaluations.
- 15. Any use of excluded medications (eg, antiepileptics, certain antidepressants or antipsychotics, antihistamines with anticholinergic properties, opiates).
- 16. Participation in clinical studies using the ISLT, BPS-O task, or the trail making test (A, B) within 1 month of screening.

Confidential Page 8 of 95

	17. Female subjects must not be pregnant, lactating, or of childbearing potential (ie, they must be 2 years postmenopause or surgically sterile).
Study Drug(s):	Subjects will receive AGB101 or placebo in the morning in identically appearing oral dosage forms. One dose of AGB101 will contain 220 mg of levetiracetam.
Duration of Treatment:	The duration of treatment will be 78 weeks.

Confidential Page 9 of 95

Main Parameters of **Primary endpoint Efficacy:** Change in CDR-SB score from baseline to 78 weeks. Secondary endpoints: cognitive/functional Change in FAQ score from baseline to 78 weeks. Change in MMSE score from baseline to 78 weeks. Secondary endpoints: neuronal injury Change in EC thickness on MRI from baseline to 78 weeks. Additional secondary endpoints Change in CDR global score from baseline to 78 weeks. Change in CDR memory box score from baseline to 78 weeks. Change in BPS-O task score from baseline to 78 weeks. Change in ISLT score from baseline to 78 weeks. Change in EC volume on MRI from baseline to 78 weeks. Change in hippocampal volume on MRI from baseline to 78 weeks. Change in [18F]MK-6240 in the brain from baseline at week 78. **Exploratory endpoint:** • Difference between treatment groups in blood-based biomarkers collected at week 78 or early termination visit. Exploratory endpoint: Functional MRI (optional procedure to be performed only at Johns Hopkins University) Confirmation of target engagement demonstrated by reduction in hippocampal overactivity. Main Parameters of Safety endpoints Safety: Change from baseline in vital signs (heart rate, respiratory rate, and blood pressure).

Confidential Page 10 of 95

	Change from baseline in physical and neurological exams.
	Change from baseline in safety labs and urinalysis.
	Change from baseline in Columbia Suicide Severity Rating Scale.
	Incidence of adverse events.
Pharmacokinetic Parameters:	AGB101 plasma pharmacokinetic sampling will be performed during the 26, 52, and 78-week visits. Time since the last dose will be recorded.
Statistical Analyses:	The primary goal of the study is to estimate the average treatment effect defined as the difference between the population mean outcome of the primary endpoint (CDR-SB change score from baseline to 78 weeks) comparing treatment to control. The primary null hypothesis is that the average treatment effect is zero. The alternative hypothesis is that the average treatment effect is not equal to zero.
	In the primary analysis, we will use a pre-specified, intention-to-treat estimator that simultaneously (i) adjusts for 78-week outcomes missing at random (due to subject loss to follow up), and (ii) adjusts for chance imbalances in key baseline variables between the study arms. One advantage of this estimator is that it is consistent under weaker assumptions on missing outcomes than needed for the unadjusted estimator to be consistent. The nonparametric bootstrap (bias-corrected and accelerated method) will be used to construct 95% confidence intervals for the average treatment effect. Similar analyses will be conducted for each of the secondary endpoints, along with a gate-keeping multiple testing procedure for an ordered sequence of null hypotheses. ApoE genotyping will be used for post hoc subject stratification. There will be a preplanned subgroup analysis in which each efficacy measure will be looked at separately by ApoE genotype with two subgroups, those carrying one or more ApoE4 alleles and those with no ApoE4 alleles.

Confidential Page 11 of 95

TABLE OF CONTENTS

1	П	NTRO	ODUCTION	21
	1.1	Bac	kground	21
	1.2	Stuc	ly Rationale	21
	1.3	Dos	e Rationale	23
	1.4	Stuc	ly Endpoint Rationale	28
	1.5	Risl	ss and Benefits for Subjects	31
2	S	TUD	Y OBJECTIVES	37
	2.1	Prin	nary Objective	37
	2.2	Sec	ondary Objectives	37
	2.3	Add	litional Secondary Objectives	37
	2.4	Exp	loratory Objectives	37
	2.5	Safe	ety Objective	37
	2.6	Stuc	ly Hypothesis	37
3	Π	NVE	STIGATIONAL PLAN	39
	3.1	Ove	rall Study Design and Plan	39
	3.2	Stuc	ly Duration	40
	3.3	Sele	ection of Study Population	40
	3	.3.1	Inclusion Criteria	40
	3	.3.2	Exclusion Criteria	41
	3	.3.3	Early Termination From Treatment	43
	3.4	Trea	atments	44
	3	.4.1	Details of Study Treatments	44
	3	.4.2	Dosage Schedule	45
	3	.4.3	Treatment Assignment (1:1 Randomization Placebo:AGB101)	45
	3	.4.4	Drug Packaging and Blinding	45
	3	.4.5	Drug Inventory and Accountability	46
	3	.4.6	Treatment Compliance	47
	3	.4.7	Prior and Ongoing Medical History and Treatments	47
	3.5	Ass	essments	47

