3 INVESTIGATIONAL PLAN

3.1 Overall Study Design and Plan

[figure not shown]
This is a multicenter, randomized, double-blind, placebo-controlled, 78-week, fixed-dose study evaluating AGB101 versus placebo as a treatment for slowing the progression of MCI due to AD.

The screening phase will occur 7 days to 42 days before the baseline visit (see Figure 4). After providing informed consent, subjects who meet entry criteria will be randomized 1:1 during the final baseline visit to receive either placebo or AGB101. A total of 160 subjects will be randomized (80/treatment group). Because of the PK and safety profile of AGB101, dosing will be initiated without titration and will be discontinued without tapering.

The baseline visit will occur 1 day before the study start. Subjects will be given their assigned study drug and instructed to take their 1st dose the next morning. A telephone contact will be made 1 week after the baseline visit to assess the subjects' medical status and inquire about any AEs/SAEs; similar telephone contacts will be made at weeks 17 and 56 with the same purpose. Study clinic visits are divided into minor visits ("clinic minor") at weeks 13, 39, and 65 and major visits ("clinic major") at weeks 26, 52, and 78. The difference between these two types of visits is the number and kinds of assessments performed. The "clinic minor" visits consist of a few basic assessments, while the "clinic major" visits consist of more in-depth testing, neuropsychological testing, and blood draws.

Subjects who enroll and subsequently discontinue the treatment before the 78-week visit will be followed up with a phone call at week 78 to assess their medical status and encourage them to come in to complete the early treatment termination/follow-up visit assessments.

Figure 4: Study Schema

Confidential Page 39 of 95

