5.2.6.2 Secondary Efficacy Endpoints

The two cognitive/functional secondary endpoints below will be tested using a fixed sequence procedure with Type I error controlled as described below.

- Secondary endpoints: cognitive/functional
 - o Change in FAQ score from baseline to 78 weeks
 - o Change in MMSE score from baseline to 78 weeks
- Secondary endpoints: neuronal injury
 - o Change in EC thickness on MRI from baseline to 78 weeks
- Additional secondary efficacy endpoints:
 - o Change in CDR global score from baseline to 78 weeks
 - o Change in CDR memory box score from baseline to 78 weeks
 - o Change in BPS-O task score from baseline to 78 weeks
 - Change in ISLT score from baseline to 78 weeks
 - o Change in EC volume on MRI from baseline to 78 weeks
 - o Change in hippocampal volume on MRI from baseline to 78 weeks
 - o Change in [18F]MK-6240 in the brain from baseline at week 78

An overall false-positive (α) rate of 5% level for the key secondary efficacy endpoints will be maintained, in that no significance of key secondary endpoints will be claimed unless the primary statistical analysis is significant at the 5% level. In addition, the testing of the key secondary endpoints will be conducted in a hierarchical fashion, in that once a null hypothesis is not rejected, all subsequent key secondary hypothesis tests will be considered exploratory. The hierarchical ordering of the secondary endpoints will be specified in the SAP prior to study unblinding.

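### The ApoE4 subgroup analysis examines carriers and non-carriers separately but never estimates the difference between their treatment effects, so a difference in significance could be misread as a difference in effect.

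*Combined protocol and SAP*

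**What the plan says.** The ApoE analysis is described only in the synopsis, under Statistical Analyses. One sentence states that "ApoE genotyping will be used for post hoc subject stratification". The next announces a preplanned analysis in which "each efficacy measure will be looked at separately by ApoE genotype with two subgroups", and names the two subgroups as "those carrying one or more ApoE4 alleles and those with no ApoE4 alleles".

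The same synopsis entry makes the average treatment effect the target of the trial and says that the BCa bootstrap "will be used to construct 95% confidence intervals for the average treatment effect". It describes no interval for a subgroup effect or for a difference between subgroup effects.

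Section 5.2.6 covers the primary endpoint, the secondary endpoints and the sensitivity analyses, and does not mention ApoE. Section 5.2.6.2 sets the rule that "no significance of key secondary endpoints will be claimed unless the primary statistical analysis is significant at the 5% level" and tests the key secondaries in sequence; the ApoE subgroups have no place in that sequence. Section 3.4.3 describes blocked randomization by site and names no ApoE stratum. Under Section 3.5.2.2 the genotyping sample is drawn at the baseline visit, which is also the randomization visit. Section 5.2 defers further detail to an SAP to be signed before database lock.

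**The concern.** Two separate analyses give two effects, each set against zero. Whether the effect depends on genotype is a different question, answered by the difference between the two effects and its uncertainty, and the supplied text does not plan that quantity.

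Without it, readers will have two estimates per measure, and perhaps two p-values, to compare by eye. The two subgroups will probably differ in size and so in power. One can then reach significance while the other does not, even when the true effects are the same. In a Phase 2B trial, such a pattern could be taken as a reason to restrict a later trial to one genotype.

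The habit is not remote. Section 1.3 contrasts the earlier phase 2 cohorts on the memory task by their separate p-values (0.041 and 0.039 against 0.2396) and quotes no between-cohort test. That observation concerns the reporting style only and implies nothing about dose.

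**Working it through.** **Inputs from the documents.** 160 subjects, 80 per arm (Section 3.1). Two-sided test, since "The alternative hypothesis is that the average treatment effect is not equal to zero" (Synopsis). 5% level (Section 5.2.6.2). Tau PET subset of about 56 (Section 3.5.4.2).

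**Assumptions, not in the documents.** Overall power of 50%, 80%, 90% or 95%; carrier share p of 50%, 60% or 70%; the same true effect in both subgroups; normal approximation; no dropout or covariate adjustment. The documents give no effect size, SD, power or dropout rate for the 160, so there is no planned figure to reproduce.

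**Step 1. Detectable effect.** Overall noncentrality = 1.96 + z(power). At 80% power this is 1.96 + 0.84 = 2.80, and 2.80 × √(2/80) = 0.443 SD.

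**Step 2. Subgroup power with equal effects.** Noncentrality is 2.80 × √p in carriers and 2.80 × √(1 − p) in non-carriers. Power a (carriers) and b (non-carriers):

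- p = 50%: 51% and 51%
- p = 60%: 58% and 43%
- p = 70%: 65% and 34%

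**Step 3. Patterns of significance.** The subgroups are disjoint, so P(exactly one) = a(1 − b) + b(1 − a), P(both) = ab and P(neither) = (1 − a)(1 − b). At p = 60% and 80% power: 0.583 × 0.575 + 0.425 × 0.417 = 0.512.

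| Overall power (assumed) | Exactly one, p = 50 / 60 / 70% | Both | Neither |
|---|---|---|---|
| 50% | 41 / 41 / 42% | 8 / 8 / 7% | 51 / 51 / 51% |
| 80% | 50 / 51 / 55% | 26 / 25 / 22% | 24 / 24 / 23% |
| 90% | 47 / 49 / 54% | 40 / 38 / 33% | 14 / 14 / 13% |
| 95% | 40 / 43 / 50% | 52 / 50 / 43% | 8 / 8 / 7% |

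At 80% overall power and given a significant overall result, simulation puts exactly one at 57%, 59% and 64%. With no effect in either subgroup it is 2 × 0.05 × 0.95 = 9.5% per measure.

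**Step 4. Precision of the missing contrast.** With n1 and n2 the per-arm subgroup sizes, the standard error of the difference is √(2/n1 + 2/n2) in SD units. Its ratio to the overall standard error is 1/√(p(1 − p)): 2.00, 2.04 and 2.18 at p = 50%, 60% and 70%. If the two effects differed by the whole 0.443 SD, the power of the contrast would be Φ(2.80/ratio − 1.96) = 29%, 28% and 25%.

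**Step 5. Tau PET subset.** 56/2 = 28 per arm. At p = 60% that leaves about 17 carriers and 11 non-carriers per arm.

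**The case against.** The plan says only that measures will be looked at separately. It states no subgroup hypothesis, p-value or significance rule, and keeps significance claims for the key secondaries inside a gated sequence that excludes the ApoE subgroups. This stands: the misreading is a risk, not a planned step. A reader might infer that discordant results will be read as a difference in effect and will decide the next trial's population, but the documents support only that they could.

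A reader might also infer that significance in one genotype only is the most likely pattern under a uniform effect. That holds only in a middle band of assumed power. At 50% power the leading pattern is neither; at 95% power with 50-60% carriers it is both. At 80% power with equal subgroups, exactly one pools two opposite patterns of 25% each.

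A reader might count 11 efficacy measures in two subgroups as 22 unadjusted tests, with a 1 − 0.95^22 = 68% chance of at least one false positive. The plan does not call them tests, and the figure assumes independence although several measures share one CDR interview or one scan. It also has no bearing on the missing contrast.

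Post hoc beside preplanned might look like a contradiction. Post hoc stratification can mean stratifying at analysis instead of at randomization, which fits Sections 3.4.3 and 3.5.2.2. The wording is ambiguous, not contradictory.

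The SAP deferred to in Section 5.2 may add a contrast; the finding applies to the text supplied. Finally, because the subgroups are disjoint, a reader given both estimates and intervals could approximate the difference. The plan promises no subgroup intervals, however, and the contrast should not be left to readers.

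**Conclusion.** The point holds for the supplied text. The plan names a subgroup method and omits the one quantity that addresses whether the effect differs by ApoE4 status. With identical true effects, discordant significance would occur about 50-55% of the time at an assumed 80% overall power and 50-70% carriers, and about 41-42% at an assumed 50% power. These are illustrations, since the documents give neither power nor carrier share.

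The change should be made but is not critical: the primary test and the gated secondaries do not depend on it. The documents do not establish that anyone will make a genotype claim from separate p-values, nor that the ApoE wording contradicts itself.

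**What to change.** In the SAP, before database lock:

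- For CDR-SB first, report the difference between the two ApoE4-specific treatment effects with a 95% BCa bootstrap interval from the same estimator as the primary analysis. Set it next to the two subgroup estimates and their intervals.
- Do the same descriptively for the other measures. Keep the tau PET subset descriptive only.
- State that heterogeneity is judged on this contrast and not on separate subgroup p-values.
- Label the analysis prespecified and exploratory, and clarify that post hoc stratification means ApoE is used at analysis and not at randomization.
- State that a null contrast is not evidence of equal effects.

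The cost is one contrast added to the subgroup analyses already planned, plus a few sentences. No procedure, sample or primary analysis changes. The small downside is imprecision: with power of about 25-29% for a difference as large as the overall detectable effect, the interval will be wide and will often include zero, which is why the last statement is needed.
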